### *Pre-Holiday Visit (v1)*

This visit occurred in HNL within a one-week period prior to Thanksgiving after an 8-12h overnight fast and 12h without exercise. Height, body weight (BW), waist and hip circumference (WC and HC), blood pressure, and body composition using Dual Energy X-Ray Absorptiometry (DXA™; Hologic Inc., Discovery A, Bedford, MA) were measured. A fasting blood draw was taken for blood lipids. Questionnaires administered at this visit included the Perceived Stress Scale (PSS), Three factor Eating Questionnaire (TFEQ), Power of Food Scale, National Insomnia Screening Questionnaire, self-weighing frequency Likert item, Mindful Eating Factors Questionnaire and Fat Preference Questionnaire. To assess participants' perceptions of healthy and unhealthy foods, participants categorized a series of 60 images of different foods accompanied by their names (e.g., pizza, pancake, and broccoli). Participants selected 'healthy' or 'unhealthy' for each food item. This was done to examine whether daily self-weighing with graphical feedback (DSW+GF) would alter subjects' perception of foods, and whether these perceptions, as well as data from our other questionnaires, would be significant mediators for the effects of DSW+GF on BW.

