#### *Post-Holiday Visit (v2)*

This visit occurred in HNL within a one-week period after New Year’s Day with the same conditions and procedures as v1. The DSW+GF group was told they could discontinue DSW; however, they were allowed to keep the scales until the follow-up visit and were told to use it as they saw fit.

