#### *Follow-up Visit (v3)*

This visit occurred in HNL 14 weeks after v2 under the same conditions and procedures as v1 and v2. The scales were collected from the DSW group and weighing frequency data during the follow-up period was obtained from their Withings® accounts. All participants were debriefed as to the true intent or purpose of the study at the conclusion of this visit.

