### **Statistical Analysis**

Statistical analyses were performed using JMP Pro 13 (Statistical Discovery™, From SAS Institute Inc., Cary, NC). A sensitivity power analysis to determine the smallest detectable effect size (was performed using G\*Power, 3.1.9.2). Assuming scores at pre-holiday were

correlated with post-holiday with at least a correlation of  $r = .40$ , our study was poised to detect differences in change scores from time 1 to time 2 of Cohen's  $f = .15$  (small-to-medium) effects. To test the treatment effects on BW across visits, as well as on the change between visits, a full factorial repeated measures ANOVA (mixed-methods) was conducted based on sex and initial BMI (normal weight (NW), and overweight and obese (OW&OB)). Participants with the BMI of 18.5-24.9kg/m^2 were categorized as NW and those with a BMI $\geq 25$ kg/m^2 were grouped into the OW&OB category. This grouping was done due to the relatively lower number of subjects in the OW or OB categories compared to NW (control group was 69% NW (n=38) and 31% OW&OB (n=17) while the DSW+GF group was 75% NW (n=42) and 25% OW&OB (n=14)). A two-way repeated measures ANOVA was used to test the treatment effects on other anthropometrics (body fat, WC, HC, and waist-to-hip ratio (WHR)), systolic and diastolic blood pressure (SBP and DBP), and blood markers (Total Cholesterol (TC), Triglyceride (TG), High-density Lipoprotein (HDL), Low-density Lipoprotein (LDL), and TC/HDL) across all visits. Post hoc analyses were performed using a Tukey's test. Significance was set at  $p < 0.05$ , and data are presented as mean  $\pm$  SEM unless otherwise specified. Additionally, data collected from questionnaires (except the Likert item), was analyzed using a parallel multiple mediator model to test whether any component of participants' responses was a mediator for the impact of treatments.

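### For the 11 non-weight outcomes, the named repeated measures ANOVA gives correct standard errors for change contrasts only if the three change variances are equal; an unstructured covariance or per-change error removes that condition cheaply

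*Combined protocol and SAP*

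**What the plan says.** There are three assessment visits. For v1: "This visit occurred in HNL within a one-week period prior to Thanksgiving". For v2: "This visit occurred in HNL within a one-week period after New Year". For v3: "This visit occurred in HNL 14 weeks after v2 under the same conditions and procedures as v1 and v2".

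For body fat, WC, HC, WHR, SBP, DBP, TC, TG, HDL, LDL and TC/HDL (11 outcomes), the Statistical Analysis section states: "A two-way repeated measures ANOVA was used to test the treatment effects on other anthropometrics". It closes that description with "across all visits. Post hoc analyses were performed using a Tukey" test. Body weight has different wording: "To test the treatment effects on BW across visits, as well as on the change between visits, a full factorial repeated measures ANOVA (mixed-methods").

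The power statement concerns two time points only. It assumes that pre-holiday scores are "correlated with post-holiday with at least a correlation of" r = .40, and says "our study was poised to detect differences in change scores from time 1 to time 2" of Cohen's f = .15.

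No covariance structure, sphericity check or correction, or error term for change contrasts is stated for any outcome. No correlation involving v3 is given.

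**The concern.** The usual repeated measures ANOVA tests every within-subject contrast against one pooled error. With three visits, each pairwise change is then judged against the average of the three change variances. A contrast whose own variance is below that average gets a standard error that is too large and loses power. One whose variance is above it gets a standard error that is too small and rejects too often.

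There is reason to doubt equality here. The intervals differ two- to four-fold. The conditions differ as well: the intervention group was asked to weigh daily over the holiday and was then free to use the scale or not. The power statement does not help, because sphericity does not arise with two time points.

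What is at stake is the comparison that locates an effect in time. A treatment-by-visit F test does not show whether groups diverged over the holiday or during follow-up; the change contrasts do.

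**Working it through.** **Inputs from the documents.** Group sizes: control 38 + 17 = 55, DSW+GF 42 + 14 = 56, total 111. Correlation v1 with v2: r = .40. Detectable effect: f = .15. Significance level: .05. Gap v2-v3: 14 weeks.

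**Input from the calendar.** Thanksgiving falls on 22-28 November. With v1 1-7 days before it and v2 1-7 days after 1 January, the v1-v2 gap is 36-54 days (5.1-7.7 weeks) and the v1-v3 gap is 19.1-21.7 weeks. I use 6.5, 14 and 20.5 weeks as central values.

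**The plan's own figure.** For the two-group, two-visit interaction, λ = f²·N·m/(1 − r) = .0225 × 111 × 2/.60 = 8.33 on 1 and 109 df, which gives 81.6% power. At 80% power the detectable f is 0.147. So f = .15 reproduces if 80% power was meant (the plan does not state the power).

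**Ratio of pooled to correct SE.** With unit variance at each visit, the variance of a change is 2(1 − r). For each contrast, k = √(mean of the three change variances / that contrast's own variance).

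**Effect on the tests.** The pooled test uses t on 2 × 109 = 218 df, critical value 1.971. A test with its own SE has 109 df and needs a noncentrality of about 2.83 for 80% power. With pooling, power is about Φ(2.83 − 1.971k) and two-sided type I error is about 2[1 − Φ(1.971k)]. All rates below are unadjusted unless stated, and leave out the sex and BMI terms. The patterns for v3 are assumptions.

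| Assumed pattern | Change variances v1-v2, v2-v3, v1-v3 | k | Consequence |
|---|---|---|---|
| A. Exponential decay from r = .40 (r = .40, .139, .056) | 1.20, 1.72, 1.89 | 1.16, 0.97, 0.92 | v1-v2 power 71%; v1-v3 type I about 7% |
| B. r = .40 for v1-v2, zero otherwise | 1.20, 2, 2 | 1.20, 0.93, 0.93 | v1-v2 power 68%; v1-v3 type I about 7% |
| C. Decay from .40, levelling off at .20 | 1.20, 1.51, 1.56 | 1.09, 0.97, 0.96 | v1-v2 power 75%; v1-v3 type I about 6% |
| D. Holiday change most variable | 2:1:1 | 0.82, 1.15, 1.15 | v1-v2 type I about 11%; other two contrasts 71% power |
| E. Equal variances | 1:1:1 | 1, 1, 1 | none |

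Worked for A: the mean variance is (1.20 + 1.72 + 1.89)/3 = 1.60, so k for v1-v2 is √(1.60/1.20) = 1.16 and power is about Φ(2.83 − 2.28) = Φ(0.55), or 71%. Over the visit windows k runs from 1.14 (7.7 weeks) to 1.18 (5.1 weeks), and power from 72% to 70%.

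Simulation with 55 v 56 and 40,000 runs agrees with these figures. Tests with their own SE held 4.8-5.2% type I error in every pattern. The omnibus treatment-by-visit F test gave 4.9-5.4% in A-C and 5.4-5.9% when the holiday change was the most variable (2:1:1 and 1.5:1:1).

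**With a Tukey value.** At the three-mean critical value of 2.36, the v1-v2 error in D becomes 2[1 − Φ(2.36 × 0.82)], about 5.5%, with familywise error about 6%. In A, v1-v3 falls to about 3% and familywise error is 5.3%.

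**The case against.** The strongest reply is that nothing here is a demonstrated error. The plan does not say that error was pooled, and the named software could have been run either way. Unequal spacing alone does not make change variances unequal: under compound symmetry the pooled error is right. Every pattern for v3 is assumed. A and B leave no stable between-person correlation at long gaps, and C, which does, costs only five points of power. At equal visit variances, D needs v3 to correlate more with v1 and v2 than they do with each other, although it is further away in time. All of this stands, and it makes the consequence conditional.

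A second reply is that, for these 11 outcomes, the plan names treatment effects across visits plus Tukey tests and mentions change for body weight only, while the omnibus test is robust. That also stands. But a treatment-by-visit effect is made up of between-group differences in change, and any statement about the holiday period rests on v1-v2.

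A reader might infer from pattern D that the plan makes false claims of a holiday effect likely. The documents do not support that. The 11% figure needs both an assumed variance pattern and unadjusted tests, whereas the plan names Tukey; at 2.36 most of the excess goes. The power loss for v1-v2 under decaying correlation is not removed by a multiplicity adjustment.

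**Conclusion.** The point holds as a cheap improvement to an incompletely specified method. For the 11 non-weight outcomes, the ANOVA in its usual form gives correct standard errors for change contrasts only under equal change variances, and the documents give no basis for assuming equality.

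The main consequence is lost precision for the holiday contrast: a standard error about 14-18% too large, and unadjusted power of about 71% instead of 80% (about 75% with a correlation floor of .20). This rests on three assumptions: pooled error, equal visit variances, and correlation that decays from the plan's r = .40. The direction can reverse if holiday change is the most variable, but inflated false-positive risk is not the main finding. If the variances are equal or separate errors were used, nothing is lost.

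It would go too far to conclude that the body-weight analysis is affected. Its reference to change between visits may already mean a separate error for each change, in which case it is sound on this point.

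**What to change.** Analyse the 11 outcomes with a mixed model that uses an unstructured covariance over the three visits; alternatively, analyse each change score with its own error. Test the between-group difference in v1-v2, v2-v3 and v1-v3 change with contrast-specific standard errors, and name v1-v2 as the contrast that matches the power statement. Do the same for body weight unless its change analysis already uses separate errors, and state which error term it uses.

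No new data are needed. An unstructured covariance has six parameters against two for compound symmetry, so four more with 111 participants. If the variances are equal, the v1-v2 test with its own SE has 79.8% power against 80.0% pooled.

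As a separate clarification, state which means the Tukey test compares. The 5% critical value is 2.36 for three means and 2.88 for six treatment-by-visit means, and a between-group difference in change is not itself a pairwise comparison of those six means.

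### The only named follow-up is an unspecified Tukey test; on group-by-visit means it contains no difference in change, so it cannot properly locate a treatment effect at v2 or v3 (mainly the 11 non-BW outcomes)

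*Combined protocol and SAP*

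**What the plan says.** All of the relevant wording is in the Statistical Analysis section.

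- **Detectable effect.** It is stated on change: "our study was poised to detect differences in change scores from time 1 to time 2", with Cohen's f = .15 and a pre/post correlation of at least .40.
- **Body weight (BW).** The aim is "To test the treatment effects on BW across visits, as well as on the change between visits", and the model is described as "a full factorial repeated measures ANOVA (mixed-methods) was conducted based on sex and initial BMI".
- **Other outcomes.** "A two-way repeated measures ANOVA was used to test the treatment effects on other anthropometrics", and also on blood pressure and blood markers, over all visits. These are body fat, WC, HC and WHR (4), SBP and DBP (2), and TC, TG, HDL, LDL and TC/HDL (5): 11 outcomes. No analysis of change is named for them.
- **Follow-up.** One sentence: "Post hoc analyses were performed using a Tukey's test". The means compared, any dependence on the interaction test, and the contrast that carries the treatment conclusion are not given.

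The visit sections give three measurement points: v1 before Thanksgiving, v2 after New Year's Day, and v3 14 weeks after v2. From v2 on, daily weighing was optional for the DSW+GF group.

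**The concern.** The treatment question is whether the arms changed by different amounts, and when. An effect at v2 is an effect of the intervention period. An effect at v3 is one present 14 weeks after daily weighing became optional. These are different conclusions, and the follow-up step has to tell them apart.

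Tukey's test compares pairs of means. On group-by-visit means, a pair is either a change within one arm or a contrast between arms at one visit, or it mixes the two. The first kind invites the inference that one arm gained and the other did not, which is not a test of treatment. The second ignores where the arms stood at v1. The follow-up could then split two arms that changed equally, or miss a difference that the study can detect when it is tested directly.

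**Working it through.** **Inputs from the Statistical Analysis section.** Arm sizes: "control group was 69% NW (n=38) and 31% OW&OB (n=17) while the DSW+GF group was 75% NW (n=42) and 25% OW&OB (n=14", so 38 + 17 = 55 control, 42 + 14 = 56 DSW+GF, N = 111. Alpha = .05, r = .40, f = .15. Three visits.

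**Assumed here.** 80% power for the sensitivity analysis (not stated), normal and complete data, compound symmetry, no sex or BMI terms. The values r = .80 and .95 are assumptions that show a range; the plan says only at least .40. SD means the between-person SD at one visit.

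**1. The plan's own figure.** For a 2-group by 2-time interaction, λ = f²·N·m/(1 − r) = 0.0225 × 111 × 2 / 0.60 = 8.325 on 1 and 109 df. Power is .816, and the smallest f at 80% power is .147. The stated .15 therefore reproduces as a test of difference in change at 80% power (90% would need .170 and 95% would need .189).

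On the SD scale this is a difference in change of 4f = 0.60 SD. The SD of change is √(2 × 0.60) = 1.095, and the SE of the contrast is 1.095 × √(1/55 + 1/56) = 0.208. The ratio is 0.60/0.208 = 2.89, and power is about .82.

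**2. What Tukey compares on six cells.** 6 × 5/2 = 15 pairs: 3 between arms at one visit, 6 within an arm across visits, and 6 differing in both arm and visit. None is a difference of differences.

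**3. What the interaction F test gives over three visits.** Under compound symmetry λ = Σ(d_j − d̄)² / [(1 − r)(1/55 + 1/56)], where d_j is the between-arm difference at visit j.

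- Effect kept to v3, d = (0, .60, .60): the sum of squares is .16 + .04 + .04 = .24.
- Effect gone by v3, d = (0, .60, 0): the sum of squares is .04 + .16 + .04 = .24.

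Both give λ = .24/(0.60 × 0.03604) = 11.1 on 2 and 218 df, and power of about .85. The F test detects both cases equally well and cannot tell one from the other.

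**4. Within-arm Tukey pairs when both arms truly change equally.** The critical |t| is the studentized range .95 quantile for 6 means and 218 df, divided by √2, which is 2.875. The SE of a within-arm change is 1.095/√55 = 0.148, so a change is declared at about 2.875 × 0.148 = 0.425 SD. If p is the chance that one arm is declared changed, exactly one arm is declared with probability of about 2p(1 − p).

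| Equal true change (r = .40) | p per arm | Exactly one arm declared changed |
|---|---|---|
| 0.30 SD | about .20 | .32 |
| 0.425 SD | about .50 | .50 |
| 0.60 SD | about .88 | .20 |

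Simulation of 20,000 trials per setting agrees, and the results are the same at r = .80 and .95 once the change is rescaled. If Tukey is read only after a significant interaction, the figures fall to .025–.042. The direct contrast is wrong in about .05.

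**5. Between-arm Tukey pair at v2 under the plan's effect.** SE = √(1/55 + 1/56) = 0.190. Power is about Φ(effect/0.190 − 2.875). The effect is rescaled so that the standardised difference in change stays the same.

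| r | Effect (SD) | Effect/SE | Tukey pair at v2 | Direct contrast |
|---|---|---|---|---|
| .40 | 0.600 | 3.16 | about .61 | about .82 |
| .80 (assumed) | 0.346 | 1.82 | about .15 | about .82 |
| .95 (assumed) | 0.173 | 0.91 | about .03 | about .82 |

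**6. Within-arm pairs under the same true effect.** The simulated chance that exactly one arm is declared changed is .88 if control gains 0.60 SD and DSW+GF 0, .32 if the split is +0.30/−0.30, and .11 if the arms gain 1.20 and 0.60. The treatment effect is identical in all three, and the direct contrast has about .82 power in each.

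**The case against.** The strongest reply is that the plan names ANOVA, not Tukey, as the test of treatment. The group-by-visit interaction in both models tests differential change, holds its 5% level and has about 85% power for the stated effect. Post hoc ordinarily means after a significant omnibus result, and with that gate the false split is at most about 4%. All of this stands. A reader might infer that the plan has no test of treatment on change; the documents do not support that.

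Three other stronger readings also fail.

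- **All 12 outcomes alike.** For BW the plan also analyses change between visits, and a comparison of arms on change would be the right contrast.
- **Tukey on cell means as the stated procedure.** Applying it to group-by-visit means is the ordinary reading after a two-way model, but it is an inference. Nothing says that Tukey was run on cells further split by sex and BMI group, so counts of pairs in that larger table have no basis. Nor does the plan say that within-arm results would be used to claim a treatment effect.
- **A power loss from putting Tukey's threshold on the difference in change.** That contrast is not among Tukey's pairs, so no such test is in the plan.

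The reply does not cover location. No gate is written. Even with one, the 2-df test leaves v2 and v3 unseparated, and cell-mean pairs would decide between them on quantities that are not the treatment effect.

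**Conclusion.** The concern holds in a limited form. The plan can detect that the arms' trajectories differ, but it does not name a comparison that measures the difference in change at v2 or at v3. If the named Tukey test is run on group-by-visit means, it does not supply one. This applies chiefly to the 11 non-BW outcomes.

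The size depends on use. Read without a gate, within-arm pairs can split equally changing arms in up to about half of trials, with the peak at an equal change near 0.425 SD at r = .40. Read after a significant interaction, the rate is under about 5% and what remains is poor localisation. The v2 between-arm pair gives up about 20 percentage points of power at r = .40 (61% against 82%) and nearly all of it if r is close to 1. The assumptions in the working apply to all of these figures. The change is one the plan should make; it does not invalidate the interaction tests.

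**What to change.** Replace the Tukey sentence with wording such as: *Treatment effects are the DSW+GF minus control differences in change from v1 to v2 and from v1 to v3, estimated as contrasts from each outcome's repeated measures model, with confidence intervals and Holm adjustment over the two. Within-arm changes are descriptive and are not used to infer a treatment effect.* For BW by sex or BMI group, use the same two contrasts within each subgroup.

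The cost is a change of wording and two contrast statements per model, with no new data. All-pairs cell comparisons are no longer inferential, and the v2-to-v3 change is descriptive unless it is added to the family. The adjustment also takes some power. At the stricter Holm step (two-sided .025, critical |t| about 2.26), the v1-to-v2 contrast has about Φ(2.89 − 2.26), or roughly 73%. Its power under Holm therefore lies between about 73% and 82%, still above the 61% of the Tukey pair at v2.
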